## **Statistical Design and Power**

Data analysis will focus on testing differences in MVPA between the Enhanced Tailored Intervention and Original Tailored Intervention at baseline, 6 and 12 months. The primary variable of interest will be MVPA (collected objectively by accelerometer). We will use a single mixed effects regression model implemented with a random intercept, in order to test both the primary question of interest (differences between arms at 6 months) and the additional aim (testing differences in MVPA during maintenance phase). Random intercepts allow for adjustment of standard errors for repeated measures of the outcome over time. Models will adjust for any variables not balanced by randomization. Analysis will be conducted on the Intent to Treat sample with all participants randomized included in the analysis. Mixed effects models use a likelihood based approach to estimation and thus do not require any direct imputation of missing outcomes. To avoid the effects of potential outliers, we will apply a normalizing transformation to the response measure (MVPA at follow-up) before proceeding with the analysis. A similar series of regression models will be used to assess between-group differences in secondary measures (self-reported MVPA, biomarkers).

As a secondary step, we will compare the efficacy of the Original Tailored Intervention in Mexican American women to the results in the original population. That is, after adjusting for study differences (including potential confounders such as acculturation, country of origin), we will compare mean minutes of MVPA between the Original Tailored Intervention (in the proposed study) and the Tailored Intervention arm (from the original parent study) using a mixed effects model, similar to that described above. Our sample size calculation is based on the assumption that we will have 80% power for testing the null hypothesis that the intention to treat effect is zero, versus the two-sided alternative that the effect is different for those randomized to the Enhanced Tailored Intervention versus those randomized to the Original Tailored Intervention. The main outcome in this case is MVPA (objectively measured) at 6 months.

Our sample size estimates are based on mean MVPA at 6 months amongst those randomized to the Tailored Intervention condition in the original parent study (R01NR011295). Mean MVPA at 6 months was 52.51 (SD=98.34) for the Tailored Intervention arm. We hypothesize that the additional enhancements in the proposed study will translate into an additional 35 min/week of MVPA at 6 months compared to the Original Tailored Intervention arm. With 125 participants randomized to each arm at baseline in the current study, we expect to have sufficient power (80%) to detect differences in mean MVPA at 6 months between the Enhanced Tailored Intervention and Original Tailored Intervention conditions, using a two-tailed significance level  $\alpha=0.05$ . In addition, given a similar assumption of an additional 35 minutes of self-reported MVPA amongst Enhanced Tailored Intervention participants relative to Original Tailored Intervention (which was 73.36 in the original parent study), the proposed sample size would also yield sufficient power (>80%) to test differences in MVPA at 6 months as collected via the 7 day PAR. It is important to note that this sample size is deliberately conservative as it does not assume the availability of repeated outcome measures that will be taken throughout the study. By choosing models that make use of the longitudinal data, we will be increasing the power to detect differences between treatment arms.

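### A random intercept is the only stated device for the standard errors; under default equal-variance residuals, the 6-month test is miscalibrated if the 6-month variance of transformed MVPA differs from the average over visits

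*SAP*

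**What the plan says.** All of the relevant text is in the SAP, Statistical Design and Power.

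- **Model:** "We will use a single mixed effects regression model implemented with a random intercept". Its purpose is "to test both the primary question of interest (differences between arms at 6 months) and the additional aim", the latter being MVPA in the maintenance phase.
- **Standard errors:** "Random intercepts allow for adjustment of standard errors for repeated measures of the outcome over time". No residual covariance structure, visit-specific variance or robust standard error is named.
- **Outcome scale:** "we will apply a normalizing transformation to the response measure (MVPA at follow-up) before proceeding with the analysis". The transformation is not named, and the reason given is outliers, not unequal spread between visits.
- **Visits:** the opening sentence has the arms compared "at baseline, 6 and 12 months", while the transformation sentence describes the response as follow-up MVPA. Whether baseline is a response row is therefore not fixed.
- **Spread:** the only accelerometer SD given is from the parent study, on raw minutes: "Mean MVPA at 6 months was 52.51 (SD=98.34) for the Tailored Intervention arm". There is none for baseline or 12 months.

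**The concern.** A random intercept accounts for the correlation between a woman's repeated values. By itself it does not let the spread differ from visit to visit. With independent, equal-variance residuals, the software default, the model has a single total variance for all visits and estimates it as an average over them. The 6-month contrast is then tested against that average and not against the 6-month variance.

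The primary test depends on this. If MVPA is more variable at 6 months than on average, the test rejects too often; if less variable, it loses power. The outcome is strongly skewed (the SD is nearly twice the mean in the parent study), so its spread could well move with the mean or with the share of women recording no MVPA. The SAP gives no reason to expect equal spread after transformation.

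**Working it through.** **The plan's own figure.** Inputs from the SAP: difference 35, SD 98.34, 125 per arm, two-sided alpha 0.05.

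- Required n per arm = 2 × ((1.96 + 0.8416) × 98.34 / 35)² = 123.9, so 124.
- Power with 125 per arm is 80.3% (normal) or 80.0% (t).

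The stated 80% reproduces. It rests on a plain two-sample comparison at 6 months, so the point below does not touch it.

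**Standard error of an arm contrast at one visit.** Assumptions: complete data, arm-by-visit means, the same variances in both arms, independent equal-variance residuals.

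- Model variance of the contrast = 2 × (mean of the visit variances) / n.
- True variance = 2 × (variance at that visit) / n.
- Ratio of model to true SE = √(mean visit variance) / SD at that visit.
- Actual type I error = 2 × (1 − Φ(1.96 × ratio)).

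**Two response rows (6 and 12 months).** Let r be the 12-month SD divided by the 6-month SD. The SE ratio is √((1 + r²)/2) at 6 months, and that value divided by r at 12 months. The values of r are assumptions.

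| r | SE ratio, 6 months | Type I error, 6 months | Type I error, 12 months |
|---|---|---|---|
| 0.8 | √0.820 = 0.906 | 7.6% | 2.7% |
| 0.9 | √0.905 = 0.951 | 6.2% | 3.8% |
| 1.0 | 1.000 | 5.0% | 5.0% |
| 1.1 | √1.105 = 1.051 | 3.9% | 6.1% |
| 1.2 | √1.220 = 1.105 | 3.0% | 7.1% |

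**What r might be after transformation.** The SAP does not say, so this is an illustration only. Assumptions: coefficient of variation 98.34 / 52.51 = 1.87 at both visits, lognormal values above zero, 20% zeros at both visits, 6-month mean 52.51, 12-month mean 42 to 63.

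- log(x+1): r runs from 0.96 to 1.04, and 6-month type I error from 5.5% to 4.6%.
- Square root: 6-month type I error from 6.3% to 4.0%.
- If the 12-month share of zeros may range from 10% to 30%, the two transformations together span 3.3% to 7.3%. The upper end pairs fewer zeros at 12 months with a lower mean, which is an unusual combination.

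**Other contrasts, two rows, complete data.** Write v6 and v12 for the visit variances, c for their covariance and v̄ = (v6 + v12)/2.

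- Change from 6 to 12 months: the model gives 2(v̄ − c) = v6 + v12 − 2c, which is the true value.
- Average over both visits: the model gives (v̄ + c)/2 = (v6 + v12 + 2c)/4, again the true value.

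In 20,000 simulated balanced datasets (125 per arm, correlation 0.5), at r = 0.8 and 1.2, type I error was 5.2% and 5.1% for the change and 5.3% and 5.1% for the average.

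**Three response rows.** The average now includes baseline, and unequal SDs can partly cancel. Relative SDs of 0.7, 1 and 1.3 give √((0.49 + 1 + 1.69)/3) = 1.03 at 6 months.

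**Check that the remedy works.** There were 2,500 simulated trials per cell (Monte Carlo SE about 0.4 points), with 125 per arm, normal outcomes, correlation 0.5 and REML. About 20% of 12-month values were missing, depending on the 6-month value. The random-intercept model gave 7.4%, 5.4% and 2.9% at 6 months for r = 0.8, 1.0 and 1.2. The unstructured covariance gave 4.6% to 5.8% over both visits and all three ratios, and 4.4% to 5.4% with complete data.

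**The case against.** The best defence is that the SAP never says the residuals have equal variance. A random intercept is compatible with visit-specific residual variances, and the SAP does not show that spread differs. That stands: the defect needs both the default fit and unequal spread, and neither is documented. But the SAP presents the random intercept as what adjusts the standard errors, so an analyst following the text would ordinarily fit the default.

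Second, the planned transformation may remove most of the problem. That also stands in part. With log(x+1) and equal shares of zeros the effect is slight; with the square root it is larger. Because the transformation is unnamed and aimed at outliers, it cannot be relied on to equalise spread.

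Third, a random intercept over two or three visits is common practice and the unstructured form is a refinement. This is fair, and it is why the point is minor.

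A reader might infer more than the document supports:

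- **That the primary test is too liberal.** The sign at 6 months is unknown; the test may equally be conservative.
- **That one of the planned tests must be too liberal.** This follows only if the maintenance test is the 12-month arm contrast. The SAP does not say so, and a change or averaged contrast has the correct SE with complete data.
- **That the error is much larger because baseline is far less variable than follow-up.** This needs baseline to be a response row and a baseline SD on the transformed scale. The SAP settles neither.
- **That estimates are biased when outcomes are missing.** The SAP does rely on the likelihood here ("Mixed effects models use a likelihood based approach to estimation and thus do not require any direct imputation of missing outcomes"), but nothing in it allows such a bias to be sized, so it is not part of this point.

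**Conclusion.** The point holds conditionally and is minor. If the single model is fitted with equal-variance residuals, and if the 6-month variance of transformed MVPA differs from the average over the response visits, the standard error of the primary contrast is wrong in a direction that cannot be known in advance. With 6 and 12 months as responses, 12-month to 6-month SD ratios between 0.8 and 1.2 move the nominal 5% to between 7.6% and 3.0%; equal spread leaves it at 5.0%. A 12-month arm contrast would err the opposite way. These sizes rest on assumed SD ratios and complete data, because the SAP gives one SD, at one visit, on the raw scale. The document therefore leaves an avoidable dependence on an untested assumption. It does not show that the primary test is invalid.

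**What to change.** Replace the random-intercept-only structure and name the response rows, for example: *Responses are transformed MVPA at 6 and 12 months, with an unstructured within-participant covariance across these visits. The primary test is the arm contrast at 6 months.* If baseline is kept as a response row, say so and use the unstructured covariance over all three visits. Each visit then has its own variance, so the primary test, and the maintenance test in whichever form it takes, no longer depends on equal spread.

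**Cost.** One sentence and a software option. Covariance parameters rise from 2 to 3 with two response rows, or to 6 with three: one to four more, easily estimated with 250 women. If the variances are in fact equal, intervals widen by about 0.5% (t with 248 degrees of freedom, 1.970 against 1.960). The sample size of 125 per arm and the 80% power stay as they are.

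### Covariates in the primary model depend on observed imbalance and baseline MVPA is not fixed, so the power gain expected from longitudinal data is not secured at 6 months

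*SAP*

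**What the plan says.** Everything relevant is in the SAP under Statistical Design and Power.

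- **Model.** "We will use a single mixed effects regression model implemented with a random intercept". This one model serves both the 6-month primary question and the maintenance-phase aim. Fixed effects are not listed.
- **Covariates.** "Models will adjust for any variables not balanced by randomization". There is no list, test or threshold.
- **Role of baseline.** The opening sentence names baseline, 6 and 12 months as the times at which arm differences are tested, which suggests that baseline is an outcome row. The transformation sentence points the other way, because it treats only follow-up as the response: "we will apply a normalizing transformation to the response measure (MVPA at follow-up".
- **Power.** The trial is sized as an unadjusted 6-month comparison. The SAP calls this conservative because repeated measures are ignored, and adds: "By choosing models that make use of the longitudinal data, we will be increasing the power to detect differences between treatment arms".

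**The concern.** There are two linked difficulties.

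First, selecting covariates by observed imbalance uses the wrong criterion. A baseline variable improves precision in a randomized comparison because it predicts the outcome, whether or not it happens to differ between arms. Baseline accelerometer MVPA is the obvious candidate. Under this rule it would usually be left out.

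Second, the SAP credits the longitudinal model with extra power, but the specification it gives does not deliver that for the primary contrast. The parts that would deliver it, baseline as a covariate or equal arm means at baseline, are neither stated nor excluded.

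At stake are precision on the primary comparison and prespecification. With no imbalance criterion, the choice between an adjusted and an unadjusted primary model can be made after arm-level data have been seen.

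**Working it through.** **Inputs from the SAP.** 125 per arm; difference 35 min/week ("an additional 35 min/week of MVPA at 6 months compared to the Original Tailored Intervention arm"); SD 98.34 ("Mean MVPA at 6 months was 52.51 (SD=98.34) for the Tailored Intervention arm"); two-sided α = 0.05; target power 80%.

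**Assumptions not in the SAP.** Correlation ρ between baseline and 6-month MVPA, varied from 0.1 to 0.7; equal SD and equal correlation across visits (what a random intercept implies); normal data on the raw-minute scale; complete data, except in step 6.

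**1. The plan's own figure.** SE = 98.34 × √(2/125) = 12.44. 35/12.44 = 2.81, and Φ(2.81 − 1.96) = 0.803; the noncentral t gives 0.800. Required n = 2 × (1.960 + 0.842)² × 98.34²/35² = 123.9, so 124 per arm against 125 planned. The 80% reproduces as an unadjusted comparison with all 250 participants measured.

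**2. What the random intercept adds.** With complete data and separate arm means at each visit, generalized least squares returns the raw difference in 6-month means, with variance 2σ²/n. This holds whether the outcome rows are 6 and 12 months or baseline, 6 and 12 months. The SE is 12.44 at every ρ. As a check, 60 fitted random-intercept models (6- and 12-month rows, ρ = 0.5) matched the raw 6-month difference to within 1e-12, with mean SE 12.40.

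**3. What baseline adds.** With baseline as a covariate, or as an outcome row with arm means constrained equal, SE = 12.44 × √(1 − ρ²). At ρ = 0.5 this is 12.44 × 0.866 = 10.77. If the test were instead change from baseline, SE = 12.44 × √(2(1 − ρ)), which beats the unadjusted comparison only when ρ exceeds 0.5.

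**4. What the imbalance rule delivers.** 100,000 simulated trials per setting, adjusting for baseline only when a 5% test found imbalance:

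| ρ | SE, separate arm means | SE, baseline used | Power, unadjusted | Power, imbalance rule | Power, always adjusted | Power, change from baseline |
|---|---|---|---|---|---|---|
| 0.1 | 12.44 | 12.38 | 80.0% | 80.1% | 80.4% | 54.9% |
| 0.2 | 12.44 | 12.19 | 80.0% | 80.3% | 81.6% | 60.3% |
| 0.3 | 12.44 | 11.87 | 80.0% | 80.7% | 83.6% | 65.9% |
| 0.5 | 12.44 | 10.77 | 80.0% | 81.1% | 89.9% | 80.0% |
| 0.7 | 12.44 | 8.88 | 80.0% | 82.1% | 97.5% | 95.1% |

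The unadjusted and always-adjusted columns are analytic (noncentral t); the rule and change columns are simulated. A looser 20% imbalance threshold raises the rule only to 83.3% at ρ = 0.5 and 86.4% at ρ = 0.7.

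**5. Type I error (simulated).** Applied mechanically at 5%, the rule is conservative: 4.8%, 4.3% and 3.7% at ρ = 0.3, 0.5 and 0.7. If the more favourable of the adjusted and unadjusted results were freely chosen, the error would be 6.4%, 7.3% and 8.3%.

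**6. With dropout.** Normal approximation, equal loss in both arms, both follow-up visits missing, ρ from 0.2 to 0.7:

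| Assumed dropout | Completers, unadjusted | Model with baseline row, arm means unconstrained | Baseline used |
|---|---|---|---|
| 10% | 76.1% | 76.3–78.1% | 77.8–96.2% |
| 20% | 71.1% | 71.5–75.5% | 72.9–94.1% |

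The unconstrained mixed model recovers about 0.2 to 4 points.

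**The case against.** The strongest reply is that nothing stated is wrong. The 80% reproduces without baseline adjustment, the rule is conservative when applied mechanically, and the power sentence is a remark about margin that gives no figure and does not name the 6-month contrast. The sample size does not rest on it. Describing the response as follow-up MVPA is also compatible with baseline entering as a covariate, so the defect is ambiguity rather than a wrong choice. With missing outcomes the mixed model does gain something over completers. Finally, ρ and the imbalance thresholds are assumed, and raw-minute figures do not carry over directly to an unspecified transformation, the more so as an SD of 98.34 against a mean of 52.51 points to strong skew.

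Much of this stands as a limit. The 80% is sound, baseline adjustment is not excluded, and the gain depends on ρ. The change-from-baseline and free-choice figures describe possible uses of an open specification, not analyses the SAP names.

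It does not remove the point. The only covariate rule the SAP states is the imbalance rule, and under it baseline usually stays out. The recovery under dropout is small beside what conditioning on baseline gives at moderate ρ. The factor √(1 − ρ²) applies on any scale, provided ρ is the correlation on that scale, so the direction survives the transformation even though the minutes do not.

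**Conclusion.** The concern holds. The primary covariate set is not prespecified, the role of baseline MVPA is left open, and the expected longitudinal gain is not secured for the 6-month contrast. Not secured is the right description; absent would be too strong.

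The loss is one of available precision: about 1 point of power at ρ = 0.2, 3 at 0.3, 9 at 0.5 and 15 at 0.7, comparing fixed adjustment with a 5% imbalance rule. These sizes rest on the assumed ρ and threshold, complete data and the raw scale. Type I error is at risk only if the model is chosen freely after seeing results. The change is worth making, but the planned test is valid without it. A model with one common effect at 6 and 12 months would also gain power, but it would no longer test the 6-month difference alone.

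**What to change.** Replace the imbalance sentence with wording such as:

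> The primary model adjusts for baseline accelerometer MVPA on the analysis scale, either as a covariate or as a repeated outcome with arm means constrained equal at baseline, and for any randomization stratification factors, regardless of observed balance. Adjustment for other imbalanced variables is a sensitivity analysis only.

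Choose one of the two forms before arm-level data are seen, and state arm-by-visit terms with the 6-month contrast named as primary. Reword the section's opening sentence so that between-arm testing applies to 6 and 12 months, with baseline listed as an assessment time.

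The cost is a few sentences and no new data. Two details need settling: the scale of the baseline covariate must suit the transformed outcome, and missing baselines need a stated method (the constrained model or a simple imputation) so that everyone randomized stays in the analysis.

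### The promise to include every randomized woman does not fit a response named as follow-up MVPA; the plan should fix the role of baseline MVPA in the primary model

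*SAP*

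**What the plan says.** All of this stands in the first paragraph of the SAP section Statistical Design and Power.

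- Analysis set: "Analysis will be conducted on the Intent to Treat sample with all participants randomized included in the analysis".
- Model: "We will use a single mixed effects regression model implemented with a random intercept". It serves both the 6-month question and the maintenance phase.
- Missing outcomes: "Mixed effects models use a likelihood based approach to estimation and thus do not require any direct imputation of missing outcomes".
- Response, as the transformation sentence names it: "we will apply a normalizing transformation to the response measure (MVPA at follow-up) before proceeding with the analysis".
- Time points, as the opening sentence lists them: "testing differences in MVPA between the Enhanced Tailored Intervention and Original Tailored Intervention at baseline, 6 and 12 months".
- Adjustment: covariates are those that turn out unbalanced after randomization. Baseline MVPA is not named as one.

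The following paragraph fixes the primary contrast: "The main outcome in this case is MVPA (objectively measured) at 6 months". The SAP does not say whether baseline MVPA is an outcome or a covariate. It states no missing-at-random assumption and gives no expected loss to follow-up.

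**The concern.** A likelihood-based mixed model can use a partly observed set of outcomes, but it cannot use an empty one. If the response is follow-up MVPA only, a woman who misses both later visits has no record in the model. Saying that imputation is unnecessary does not bring her back. Two statisticians following this paragraph could therefore analyse different numbers of women, and both could report that all randomized participants were included.

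The head count is the smaller part of the problem. With a follow-up-only response and adjustment only for unbalanced variables, a trial whose arms look balanced on baseline MVPA would not use baseline MVPA at all. If the women who leave differ in baseline activity between arms, for example if less active women leave one arm more readily, the women who remain are no longer comparable. The plan would then leave out the variable that corrects for this.

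**Working it through.** **1. The plan's own figure.** Inputs from the sample-size paragraph: difference 35 min/week, SD 98.34, two-sided alpha 0.05, power 80%.

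n per arm = 2 × (1.960 + 0.842)² × (98.34/35)² ≈ 124, against 125 stated. Power at 125 per arm is 80.3% (normal) or 80.0% (noncentral t). The figure reproduces, so 35 and 98.34 are used below.

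**2. Who enters the likelihood.**

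| Accelerometer values present | Response = 6 and 12 months | Response = baseline, 6 and 12 months |
|---|---|---|
| Baseline and at least one follow-up | in | in |
| Baseline only | out | in |
| None | out | out |

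Only the second row depends on the reading of the plan. If 10% to 20% of women had no follow-up value (an assumption), that row would hold 0.10 × 250 = 25 to 0.20 × 250 = 50 women.

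One simulated trial of 250 women, 30 of them without either follow-up, shows the count. The follow-up-only fit with baseline as a covariate used 220 women and gave a 6-month difference of 14.6 (SE 11.26). The fit with baseline in the response used 250 and gave 14.8 (SE 11.29). The number of women changed and the result hardly did. Both fits used baseline, which the plan does not guarantee.

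**3. Bias when baseline is not used.** Assumptions, none of them from the SAP:

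- standardized baseline x is normal and linearly related to 6-month MVPA, with correlation r of 0.2 to 0.6;
- a fraction L of each arm, 10% or 20%, has no follow-up;
- the log odds of loss change by β per SD of baseline, with β = −0.5 or −1 in the enhanced arm and 0 or +0.5 in the other;
- the scale is untransformed min/week with SD 98.34.

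With p(x) the probability of loss, the mean of x among women who stay is

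shift = −β × E[p(1 − p)] / (1 − L),

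and the bias of the 6-month difference is

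bias = r × 98.34 × (shift in enhanced arm − shift in other arm).

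- Mildest case (L = 10%, r = 0.2, β = −0.5 against 0): E[p(1 − p)] = 0.0879, so the shifts are 0.5 × 0.0879/0.9 = 0.0488 and 0. Bias = 0.2 × 98.34 × 0.0488 = 0.96 min/week.
- Most severe case (L = 20%, r = 0.6, β = −1 against +0.5): the shifts are 1 × 0.1386/0.8 = 0.1732 and −0.5 × 0.1539/0.8 = −0.0962. Bias = 0.6 × 98.34 × 0.2694 = 15.9 min/week.

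As shares of the planned effect, these are 0.96/35 = 3% and 15.9/35 = 45%. Simulation of the same grid gave about 0.6 to 16 min/week. With 400,000 women per arm the simulation standard error is about 0.23, so 0.6 and 0.96 agree within simulation error.

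**4. The same mechanism with baseline used.** Equal β and equal loss in the two arms give equal shifts, so the bias is zero. If loss depends only on baseline, 6-month MVPA given baseline is the same in those who stay and those who leave. With baseline in the model as response or as covariate, the simulated bias was within about 0.5 min/week of zero in every scenario, whether or not women without follow-up were counted.

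**The case against.** The strongest reply is that the exclusion is not certain. The follow-up wording is a parenthesis in a sentence about outliers, whereas the opening sentence lists baseline among the time points and the model is justified by repeated measures over time. If baseline is in the response, every woman with a baseline record contributes. This stands, and it makes the fault an inconsistency rather than a proven exclusion. It does not remove the fault: the parenthesis is the only place where the response is named, and transforming follow-up values alone fits poorly with a response that also contains baseline.

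A reader might infer that the trial does not analyse its intention-to-treat population. The documents do not support that. Analysing all observed outcomes by assigned arm with a likelihood model is an accepted approach under missing at random, the sentence on imputation is sound under that assumption, and a woman with one of the two follow-up visits stays in.

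A reader might also infer that the bias comes from leaving women out. It does not: with the same women left out and baseline as a covariate, it is about zero. The cause is the missing commitment to baseline.

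It is also fair to say that the SAP gives no loss rate and no sign of loss that differs by arm, so the bias is conditional. Nothing in the SAP points to missing covariate values. Not using the 7-day PAR in the primary model is no error, since self-reported MVPA is a secondary measure.

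**Conclusion.** The concern holds as an internal inconsistency of minor severity. The plan promises that all randomized women are included, names a response under which some may not be, and does not commit to baseline MVPA in any role.

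The possible bias, from just under 1 to about 16 min/week against the planned 35, rests on the assumed loss, correlation and arm-specific dependence on baseline, and on a linear relation on the untransformed scale. It shows what could happen and does not predict what will. The near-zero bias with baseline in the model rests on loss depending on baseline alone and on the model describing the relation between visits adequately. It says nothing about loss that depends on unobserved follow-up activity.

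**What to change.** Preferred: state that the response is accelerometer MVPA at baseline, 6 and 12 months, all on the same transformed scale, with arm-by-time terms and the 6-month arm difference as the primary contrast. Every woman with a baseline record then contributes. A woman with no valid accelerometer record at any visit still would not, so the number contributing per arm should be reported.

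Alternative: keep a follow-up-only response, include baseline MVPA as a covariate whatever the observed balance, and replace the all-randomized wording. The analysis would then cover randomized participants with at least one follow-up value, by assigned arm, assuming missing at random.

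Either change costs one or two sentences and little programming, and needs no new data, as baseline is already among the plan's listed time points. Multiple imputation that draws on the 7-day PAR is optional.

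### The 80% power needs a 6-month value from essentially every randomized woman, and the reserve claimed from repeated measures is not secured by the model as specified

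*SAP*

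**What the plan says.** Everything relevant stands in the SAP under Statistical Design and Power.

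- **Sizing.** The plan takes a 6-month mean of 52.51 (SD 98.34) from the parent study's tailored arm, a hypothesised gain of 35 min/week and a two-sided 0.05 level. It concludes: "With 125 participants randomized to each arm at baseline in the current study, we expect to have sufficient power (80"%). The number attached to the power is the number randomized.
- **Reserve.** The plan says that "this sample size is deliberately conservative as it does not assume the availability of repeated outcome measures", and adds: "By choosing models that make use of the longitudinal data, we will be increasing the power to detect differences between treatment arms". It gives no correlation and no resulting power.
- **Model.** "We will use a single mixed effects regression model implemented with a random intercept". The focus is on "testing differences in MVPA between the Enhanced Tailored Intervention and Original Tailored Intervention at baseline, 6 and 12 months", with the arm difference at 6 months as the primary question. Elsewhere the response is described as follow-up MVPA. On covariates: "Models will adjust for any variables not balanced by randomization". Baseline MVPA is not named as a covariate, and no model terms are listed.
- **Missing data.** "Analysis will be conducted on the Intent to Treat sample with all participants randomized included in the analysis". Mixed models are said to be likelihood based and "thus do not require any direct imputation of missing outcomes".

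**The concern.** The sizing leaves no margin: the number of women needed with a 6-month value is practically the number randomized. Yet the plan foresees missing outcomes. Keeping every randomized woman in a likelihood analysis avoids imputation. It does not give a woman without a 6-month value the information of one who has it.

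The plan's answer is that repeated measures supply a reserve. Whether they do so for a 6-month contrast depends on how baseline is used, and the text allows several readings. Baseline could be an outcome with its own arm difference, an outcome with equal arm means, a covariate, or left out of the model. Some of these give a real gain and others almost none. At stake is the power of the primary comparison and the accuracy of the statement made about it.

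**Working it through.** **Inputs from the SAP.** Difference 35 min/week; SD 98.34, taken as common to both arms; two-sided 0.05; 125 randomized per arm.

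**Assumptions, not in the SAP.** Loss d of 5% to 20%; correlation ρ between visits of 0.3 or 0.5. Everything is on the raw-minute scale used for the sizing. The planned normalizing transformation is not modelled.

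**1. Reproduce the 80%.**

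n per arm = 2 × (1.96 + 0.8416)² × 98.34² / 35² = 123.9, so 124.

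Power at 125 (normal): standard error = √(2 × 98.34² / 125) = 12.44; 35 / 12.44 = 2.814; Φ(2.814 − 1.96) = 80.3%. The noncentral t gives 80.03% at 125 and 79.7% at 124. The SAP's figure is confirmed for complete data.

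**2. Observed values only, 125(1 − d) per arm, noncentral t.**

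| Loss | Women per arm | Power | Difference detectable at 80% power (min/week) |
|---|---|---|---|
| 0% | 125 | 80.0% | 35.0 |
| 5% | 118.75 | 78.0% | 35.9 |
| 10% | 112.5 | 75.7% | 36.9 |
| 15% | 106.25 | 73.3% | 38.0 |
| 20% | 100 | 70.7% | 39.2 |

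**3. Planned random-intercept model.** Visits are at 0, 6 and 12 months with equal correlation ρ. All women have baseline, and women missing month 6 also miss month 12. Normal approximation throughout.

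- *Free arm-by-visit means.* Variance of the 6-month arm difference = 2 × SD² × [(1 − ρ²) / (n(1 − d)) + ρ² / n]. With d = 0 this is 2 × SD² / n whatever ρ is, so nothing is gained.
- *Baseline adjusted for, or baseline arm means equal.* Variance = 2 × SD² × (1 − ρ²) / (n(1 − d)).

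Example at d = 0.15, ρ = 0.5, with 2 × 98.34² = 19,341.5:

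- Free: 19,341.5 × (0.75/106.25 + 0.25/125) = 175.2; standard error 13.24; Φ(35/13.24 − 1.96) = 75.3%.
- Adjusted: 19,341.5 × 0.75/106.25 = 136.5; standard error 11.68; Φ(35/11.68 − 1.96) = 85.0%.

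| Loss | Observed only (normal) | Free, ρ 0.3 | Adjusted, ρ 0.3 | Free, ρ 0.5 | Adjusted, ρ 0.5 |
|---|---|---|---|---|---|
| 0% | 80.3% | 80.3% | 83.9% | 80.3% | 90.1% |
| 10% | 76.1% | 76.5% | 79.9% | 77.1% | 86.9% |
| 15% | 73.7% | 74.3% | 77.6% | 75.3% | 85.0% |
| 20% | 71.1% | 71.9% | 75.1% | 73.3% | 82.8% |

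At 15% loss the choice is worth 77.6 − 74.3 = 3.3 points at ρ 0.3 and 85.0 − 75.3 = 9.7 points at ρ 0.5. If month 12 is observed for women who miss month 6, the ρ 0.5 figures become 75.9% and 85.6%, a move of under 1 point.

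**4. Correlation needed to restore 80% with baseline adjusted.** ρ = √(1 − 125(1 − d)/123.9), which gives about 0.20, 0.30, 0.38 and 0.44 at 5%, 10%, 15% and 20% loss.

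**The case against.** The strongest reply has four parts.

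- **A retention rate often sits in the protocol, which is not shown.** True, and its absence from the SAP is not the point made here. The point is that the SAP's own 80% at 125 randomized leaves no room for any loss rate, wherever that rate is stated.
- **The loss rates and correlations are assumed, and the test is on a transformed scale.** This stands. The percentages illustrate size and do not describe this trial. The 10-point figure in particular needs ρ of 0.5; at 0.3 it is about 3 points.
- **Ignoring repeated measures is at worst neutral, so the claim errs in the right direction.** For the stated 6-month contrast this is fair: none of the cases above falls below the analysis of observed values alone. But a neutral result is not a reserve, and the plan says without condition that power will increase.
- **Several parameterisations of a mixed model are valid.** Also true. They differ in efficiency, though, and the claimed gain depends on which is chosen.

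Two stronger readings are tempting but unsupported. A reader might infer that the primary test could be coded as change from baseline, where a low correlation would push power below the two-sample figure. The SAP names the arm difference at 6 months as the primary question and 6-month MVPA as the main outcome, so that reading conflicts with the text. A reader might also infer that the SAP makes adjustment for baseline MVPA depend on observed imbalance. The covariate sentence neither mentions baseline MVPA nor says that only unbalanced variables will be used. The plan leaves baseline handling open.

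**Conclusion.** The concern holds in two parts. The first rests on the SAP's figures alone: 80% power requires 124 to 125 women per arm with a 6-month value, and 125 are randomized, so nothing covers the missing outcomes the plan foresees. The second is that the claimed reserve is unquantified and unsecured. With free arm-by-visit means, the 6-month comparison gains nothing when data are complete and little when they are not. With baseline adjusted or constrained, the gain is real. At an assumed 15% loss this means 74% to 75% against 78% to 85% for ρ between 0.3 and 0.5, on raw minutes with equal correlation between visits.

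It does not follow that the trial is underpowered. With good retention, or a moderate correlation and baseline in the model, power can reach or exceed 80%. This should be fixed because the primary test is affected and the correction is cheap.

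**What to change.** 1. **Fix the baseline term.** Suggested wording: *Baseline MVPA, on the analysis scale, is always adjusted for in the primary model (or baseline arm means are constrained to be equal); the primary test is the arm difference at 6 months.*
2. **Restate the power.** Suggested wording: *125 per arm gives 80% power (difference 35, SD 98.34) if every randomized woman has a valid 6-month accelerometer value; at the expected valid-data rate of X%, unadjusted power is Y%, or the detectable difference is Z.* At 85% valid data, for example, Y is about 73% and Z about 38 min/week.
3. **Support or delete the conservative claim.** Keep it only with a stated baseline-to-6-month correlation and the resulting power. At 85% valid data with baseline adjusted, for example, that is about 78% at a correlation of 0.3 and 85% at 0.5. Otherwise remove it.

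The cost is SAP wording and one fixed model term, using the baseline measurement already planned. No participants or visits are added. The stated unadjusted power becomes less favourable, and any gain claimed must rest on a stated correlation.
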